If an admission was in the intervention arm in the intervention period, then their ES-DOT per at-risk day was reduced by a proportion, given below. The reduction of ES-DOT per at-risk day was selected with a lower bound determined by the investigators as the hoped-for effect of the intervention with minimal clinical significance, and the impact in the Monte Carlo calculation on a per-admission basis was to reduce the days of therapy proportionately between this number and 1, on a uniform distribution. In other words, if the effect of the intervention was to multiply doses by as little as .9, each person would have their doses multiplied by between .9 and 1. Then an integer value of doses would be chosen as described above.

We are interested in determining whether the patient-specific CPOE intervention reduces ES-DOT per at-risk day by at least 12.5% relative to usual care. Using the method above, we have 97% power (CI 91-99%) to detect this effect. **Table 5** below shows the calculated power and confidence intervals for the primary and secondary outcomes to be evaluated in our primary manuscript.

Primary Trial OutcomePower (Cl), %Extended-Spectrum Antibacterial Days Of Therapy
(ES-DOT) per Empiric Day97 (91-99)Secondary Trial Outcomes92 (85-96)Vancomycin Days of Therapy per Empiric Day92 (85-96)Antipseudomonal Antibiotic Days Of Therapy (ES-
DOT) per Empiric Day84 (77-91)

Table 5. Power Calculation – Primary and Secondary Outcomes

References Cited

- 3. Centers for Disease Control and Prevention. Antibiotic Resistance Threats in the United States, 2013. Available at: http://www.cdc.gov/drugresistance/pdf/ar-threats-2013-508.pdf. Accessed on May 19, 2015.

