The INSPIRE-ASP Trial is a two-arm cluster-randomized trial in HCA hospitals comparing routine empiric antibiotic prescribing for patients admitted with UTI to prescribing informed by pointof-care precision medicine computerized physician order entry (CPOE) smart prompt for adult patients admitted to general medical or surgical floors. The unit of randomization will be the hospital. The trial will begin with a six-month phase-in period from October 1, 2018-March 31, 2019, followed by a 15-month trial intervention period between April 1, 2019-June 30, 2020. For analysis purposes, the cohort will be defined as adult patients with a primary or secondary claims code indicating UTI that is present on admission, did not transfer directly from the ED to ICU, and is treated with an antibiotic within the first 3 days of hospitalization. A baseline period between April 1, 2017-September 30, 2018 will be utilized for comparison with the intervention period at each hospital. Per guidance from the Office for Human Research Protections (OHRP), prisoners will not be included in this trial. Prescribers and antibiotic stewardship teams in intervention facilities will be trained (e.g., coaching calls, usual communication channels (email, flyers)) that prisoners should be excluded from the trial (i.e., the CPOE smart prompt should not be acted upon for these individuals). Data for any prisoners that may be inadvertently included in study datasets will be removed prior to analyses using claims data as well as admission/discharge/transfer codes indicating 'Court/Law Enforcement'.

B.1.2 HCA Healthcare Infrastructure for the INSPIRE-ASP Intervention Arm

HCA Healthcare currently requires physicians to provide an indication when an antibiotic is ordered (see **Appendix B** for example CPOE indication screens). For facilities assigned to the intervention arm of the INSPIRE-ASP Trial, an INSPIRE CPOE smart prompt will be triggered when physicians prescribe an extended-spectrum (ES, **Table 1**) for a UTI indication in the first three days of a hospital stay. This CPOE smart prompt will provide clinicians with a patient-specific estimate of the likelihood that the UTI is due to the associated target pathogens (e.g. MRSA, VRE, Pseudomonas, ESBL, or CRE, **Table 1**). The smart prompt will also provide guidance for appropriate empiric antibiotic options per trial protocol and hospital policy.

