¹E.g., if a patient is admitted for 2 days, ES-DOT will be calculated for 2 days and divided by 2 empiric days; conversely if a patient is admitted for 4 days, only the first 3 days will be evaluated. ²Does not include aminoglycosides or fluoroquinolones.

Safety outcomes planned for the primary manuscript are shown in **Table 4**. Safety outcomes will be analyzed separately from the main effectiveness outcomes of the trial (see Primary Statistical Analysis section below).

Table 4: Other Pre-Specified Outcomes – Safety Trial Outcomes

Safety Trial Outcomes (other pre-specified outcomes)				
Antibacterial Escalations [Safety	Days from start of standard-spectrum antibacterial until switch to			
Outcome]	extended-spectrum antibacterial during hospital stay			
ICU Transfers [Safety Outcome]	Days from start of hospitalization until ICU transfer within hospital stay			
Length-of-stay [Safety Outcome]	Days from hospital admission to discharge			

B.1.10 Analysis

The primary trial outcome is defined as the summed number of different extended spectrum antibiotics received each day, measured repeatedly over the first three days of an admission and divided by the number of days of the admission within the empiric period. An empiric day is a day

within the first three days of an admission. We define this outcome as an Extended-Spectrum Days Of Therapy (ES-DOT) per empiric day. For clarity the calculation is as follows: we define a DOT for a particular ES antibiotic as a day in which any number of doses of that antibiotic is given. Different ES antibiotics are summed across the empiric days for each patient admission, then divided by the empiric days for that patient-admission to determine each admission's DOT per at-risk day. If an admission is less than 3 days, only the number of days the patient is admitted will contribute to the numerator and denominator. Antibiotics given during an associated emergency department visit on the date of hospital admission are counted toward the ES-DOT of the first hospital day.

The main trial results will be based upon as-randomized, unadjusted analyses of admissionlevel ES-DOT per empiric day. We define ES-DOT per empiric day at the individual admission level so that we can perform analyses on individuals.

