The assessment of trial success will be determined by the significance of the arm by period interaction term β 3, which assesses whether the log relative rate of the outcome due to being in the intervention arm in the intervention period is different from 0. The exponentiated parameter estimate for β 3 is the estimated relative rate of ES-DOT per at-risk day due to the intervention, relative to the baseline period. For example, if β 3 had a negative value and a p- value <0.05, we would conclude that the patient-specific CPOE smart prompts generated a benefit over routine care. Exponentiating the parameter value would provides an estimate of the relative reduction due to the intervention in the expected ES-DOT per at-risk day.

The primary trial analysis will use an as-randomized unadjusted model with two-tailed significance set at alpha = 0.05. Secondary outcomes also will be assessed using an as-randomized unadjusted model with adjustment for multiple comparisons with two-tailed significance set at alpha = 0.025 for the two secondary outcomes. Subsequent analyses of the primary and secondary outcomes will include both as-treated and adjusted models. Adjusted models will account for individual characteristics such as age, gender, comorbidities, and prior history of MDROs as well as hospital characteristics such as hospital antibiotic resistance. We will also account for randomization unit and for seasonality. These analyses will be reported as point estimates with confidence intervals without p-value. The reason for including these analyses is to provide additional information related to the trial outcomes for readers to assess the effects of potential confounders. The reason to not include them in a formal multiple comparisons adjustment

is because these analyses are non-independent evaluations relative to the as-randomized unadjusted analyses.

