Safety outcomes noted in the below table will be assessed in the most conservative manner to identify potential safety issues. This is required because a reduction in ES-DOT might be achieved only by incorrectly withholding ES antibiotics when they were really needed. Each safety outcome will be evaluated for non-inferiority using an as-randomized unadjusted model with a one-tailed significance set at alpha = 0.05. Analyses planned for these assessments are proportional hazards models with random effects (to account for hospital effects). These models are sometimes called frailty or shared frailty models. Because these are safety outcomes, we do not intend to make adjustments for multiple comparisons in testing them, further increasing conservatism.

All analyses will be performed using current versions of SAS (Version 9.4, as of writing, SAS Institute, Cary NC) and/or R (Version 4.0, as of writing).

B.1.11 Power Size/Sample Size Calculations

Power assessment proceeded as follows, using a Monte Carlo approach. We used available data to define a baseline period of 10/1/2015-12/31/2016 in a bootstrap procedure. Individuals were selected with replacement from within each hospital, once to represent baseline data and separately to represent intervention period data. In the randomization portion of the Monte Carlo approach, we ordered the hospitals by "size", meaning the number of admissions with UTI. Then, within strata of 6 hospitals, we ordered by ES-DOT per at-risk day. Then we took pairs of hospitals with adjacent ES-DOT per at-risk day and assigned one member of the pair to one arm. To do this, a single pseudo-random number uniformly distributed between 0 and 1 was generated for each pair. If it was less than 0.5, the arbitrary "first" member of the pair was assigned to Routine Care and the other to Intervention. If it was greater than or equal to 0.5, then the assignments were reversed. The remaining unpaired hospital of the 59 units were assigned as the "first" member of a pair with no match. (Three sets of hospitals each shared a stewardship program and these hospitals were treated as a single hospital within the routine.)

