## • Arm 1 – Routine Care

## • Arm 2 – Real-Time Risk Estimation Smart Prompt

Precision medicine smart prompt using a computerized physician order entry (CPOE) alert that gives a patient-specific risk estimate of antibiotic resistant infection and recommends standard-spectrum antibiotics in patients admitted for UTI who are found to have low risk (<10%) for recovery of a drug resistant pathogen.

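### No safety outcome counts in-hospital death, and the plan does not say how death is handled in the ICU-transfer and length-of-stay tests

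*Protocol*

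**What the plan says.** Protocol section B.1.9, Table 4, and the SAP section on trial outcomes, Table 2, list the same three safety outcomes:

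- Escalation: "Days from start of standard-spectrum antibacterial until switch to" an extended-spectrum (ES) antibacterial.
- ICU transfer: "Days from start of hospitalization until ICU transfer within hospital stay".
- Length of stay: "Days from hospital admission to discharge".

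The lead-in limits the scope of the table: "Safety outcomes planned for the primary manuscript are shown in" it.

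On analysis, Protocol B.1.10 and the SAP's Primary Statistical Analysis section say: "Each safety outcome will be evaluated for non-inferiority using an as-randomized unadjusted model", at one-sided alpha 0.05, with proportional hazards models that include hospital random effects. The stated reason is that ES days of therapy could fall because needed ES drugs were wrongly withheld. Neither section gives a non-inferiority margin, a censoring rule or a rule for competing events.

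Mortality appears in the Protocol's background sections and in reference titles. It is not listed as a trial outcome in either document as supplied.

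On the intervention, Protocol B.1.2 says "an INSPIRE CPOE smart prompt will be triggered when physicians prescribe an extended-spectrum" drug for a UTI indication. The SAP's Arm 2 description says the prompt "recommends standard-spectrum antibiotics in patients admitted for UTI who are found to have low risk".

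**The concern.** If needed ES drugs are withheld, death on the ward is the gravest harm that could follow, and the planned safety outcomes do not capture it. A patient who dies on the ward without earlier ICU transfer contributes no ICU event. If death closes the stay, that patient can also be recorded as discharged, and earlier discharge is the favourable direction. Safety tests meant to detect withholding harm could therefore show nothing while ward deaths rise.

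The secondary concern is the escalation clock. An admission that receives only ES drugs has no time origin, so only admissions that receive a standard-spectrum drug can be at risk. Receiving one is decided after randomization, and the prompt exists to change that decision. The two arms may then be comparing different kinds of patient.

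**Working it through.** The plan states no figure for this point, and it gives no rates for death, ICU transfer, escalation or standard-spectrum starts. **Every rate below is assumed.**

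**1. ICU transfer, ward deaths doubled.** Let *icu* be the proportion transferred and *w* the proportion dying on the ward without transfer. Transfers are held fixed.

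Composite HR = ln(1 − (icu + 2w)) / ln(1 − (icu + w))

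| icu | w | Composite HR, deaths ×2 |
|---|---|---|
| 8% | 0.4% | ln(0.912)/ln(0.916) = 1.050 |
| 5% | 0.8% | ln(0.934)/ln(0.942) = 1.143 |
| 3% | 1.2% | ln(0.946)/ln(0.958) = 1.294 |

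With deaths raised by 50%, the first and last rows give 1.025 and 1.146. A constant-hazard simulation with 2,000,000 admissions per arm, censoring deaths and discharges, gave ICU-transfer HRs of 0.998, 0.998 and 0.999, and composite HRs of 1.045, 1.135 and 1.287. The ICU-transfer value near 1 follows from holding transfers fixed. It shows what the endpoint cannot see, not that harm would take this form.

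**2. ICU transfer, other patterns of harm.**

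- Both rise by 50% (icu 5%, w 0.8%): ICU-transfer HR ln(0.925)/ln(0.95) = 1.52; composite HR ln(0.913)/ln(0.942) = 1.52. Nothing is lost by using ICU transfer alone.
- Only ICU transfer rises, by 10% (icu 3%, w 1.2%): ICU-transfer HR ln(0.967)/ln(0.97) = 1.10; composite HR ln(0.955)/ln(0.958) = 1.07. The composite dilutes the signal.

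**3. Length of stay.** Take a live-discharge hazard of 0.22 per day and a death hazard rising from 0.003 to 0.006 per day. In-hospital death then rises from 0.003/0.223 = 1.35% to 0.006/0.226 = 2.65%.

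- Death counted as discharge: HR = 0.226/0.223 = 1.013.
- Death censored: HR about 1.00 (0.999 simulated).
- Death kept in the risk set as never discharged: HR 0.958 (simulated).

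With gamma-distributed stays (mean 4.5 days) and decedents' stays averaging 3, 4.5 or 9 days, counting death as discharge gave 1.007, 1.001 and 0.982. Censoring it gave 0.994, 0.988 and 0.970. Keeping deaths in the risk set gave 0.95 each time. The contrast is therefore 0.97 to 1.01 against 0.95 to 0.96.

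**4. Escalation.** Assume a share *s* of control admissions start standard-spectrum and the prompt moves a fraction *m* of ES starters. Usual starters escalate at 0.03 per day over three days, so r0 = 1 − exp(−0.09) = 0.0861. Moved patients make up w' = m(1 − s)/(s + m(1 − s)) of the intervention-arm risk set.

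Example with s = 0.5 and m = 0.2: w' = 0.1/0.6 = 0.167. If moved patients have half the usual hazard, their risk is 1 − exp(−0.045) = 0.0440. The mixed risk is 0.833 × 0.0861 + 0.167 × 0.0440 = 0.0791, and the apparent HR is ln(1 − 0.0791)/ln(1 − 0.0861) = 0.915. At twice the usual hazard it is 1.161.

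Over s of 40–60%, m of 10–30% and hazard ratios of 0.5 to 3 for moved patients, the apparent HR runs from 0.84 to 1.58 with no change in any patient's hazard. With s = 0.5 and moved patients at half the hazard, a true 10% rise in everyone's hazard shows as 1.006 (m = 0.2) or 0.971 (m = 0.3).

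**The case against.** **Most of the safety package is free of selection.** ICU transfer runs from hospitalization and length of stay from admission, so neither depends on drug choice, and no text rests safety on escalation alone. This stands, and it is why escalation is only the secondary point.

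**The ICU result depends on the pattern of harm assumed.** This also stands. Where harm raises transfers and deaths together, ICU transfer alone detects it. The loss is confined to excess ward deaths that are not accompanied by more transfers.

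**The length-of-stay effect is small.** Agreed. If decedents have long stays, counting death as discharge can even move the HR slightly below 1.

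**The tables cover only the primary manuscript.** They do, but neither supplied document plans a mortality analysis elsewhere. The SAP text ahead of its Background section was not available; an outcome definition there is unlikely but cannot be excluded.

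**Stronger readings that a reader might infer.**

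- *The escalation test is tilted towards hiding harm.* The documents do not settle the direction. It depends on whether moved patients escalate less or more than usual starters, and values above 1 may partly reflect a real later need for ES drugs.
- *The as-randomized label is wrong.* It is not. Hospitals are analysed in their assigned arm; for the primary and secondary outcomes the plan contrasts this with later analyses that "will include both as-treated and adjusted models". The label fixes the arm but does not make a group selected after randomization comparable.
- *More escalations per admission would show harm.* They would not. Suppose 60% start standard-spectrum, 6% of them escalate, and a further 5% of admissions are moved and escalate at 3%. Escalations per admission rise from 3.60% to 3.60% + 0.15% = 3.75%, while admissions ever given ES drugs fall from 40% + 3.6% = 43.6% to 35% + 3.75% = 38.75%.
- *The 12.5% in the power section gives the share of patients moved.* It is a reduction in ES days of therapy, so it was not used as the share moved in the escalation range above.

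**Conclusion.** The point holds for death. As supplied, the plan neither counts in-hospital death as a safety outcome nor says how it enters the ICU-transfer and length-of-stay models. Excess ward deaths would leave the ICU-transfer HR near 1.00 if transfers do not also rise, where a composite would give 1.05 to 1.29 for doubled deaths. The length-of-stay HR would stay at 0.97 to 1.01, against 0.95 to 0.96 when deaths are kept in the risk set, at assumed death rates of about 1–3%. The main loss is undetected deaths, not a distorted length-of-stay estimate.

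For escalation, the supportable conclusion is narrower. The HR is conditional on a standard-spectrum start, can be biased either way, and is not a comparison of like patients.

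The documents do not support saying that a non-inferiority verdict would be wrong: no margin is stated, so the effect on pass or fail cannot be judged. All sizes rest on assumed rates. The change is worth making before analysis; the primary outcome is not affected.

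**What to change.** 1. Report in-hospital death by arm and period.
2. Analyse ICU transfer or in-hospital death, whichever comes first, in all cohort admissions, with ICU transfer alone beside it.
3. Define the length-of-stay event as discharge alive, keep deaths in the risk set as never discharged, and state that an HR below 1 is the harmful direction.
4. Label the escalation analysis as conditional on a standard-spectrum start, and report standard-spectrum starts by arm and period. Escalations per cohort admission may be added as description only, because they rise mechanically as more patients start standard-spectrum drugs.

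The cost is SAP wording and endpoint programming; no planned test is removed. It assumes that the claims or admission/discharge/transfer data carry death status. Protocol B.1.1 names those sources for removing prisoners and does not confirm this. The composite has two downsides: unrelated deaths add noise, and an effect on ICU transfer alone is somewhat diluted (1.10 to 1.07 in the example), which is why ICU transfer should be shown beside it.

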# Background

The **INSPIRE-ASP Urinary Tract Infection (UTI) Trial** (INtelligent Stewardship Prompts to Improve Real-time Empiric Antibiotic Selection for Patients with UTI) is a cluster-randomized trial of HCA Healthcare (HCA) affiliated hospitals to assess best practice in antibiotic stewardship for adult hospitalized patients admitted to non-critical care units with UTI. It compares routine care to the use of a real-time smart prompt that provides a patient's specific risk of antibiotic-resistant UTI and alerts the clinician during the antibiotic ordering process to optimize prescribing and ideally improve patient outcomes. The main goal is to see if there is a difference in the empiric antibiotic prescribing practices for extended-spectrum antibiotics (ES). We define antibiotics administered during the first three days of hospitalization as empiric treatment because infecting pathogens and their antimicrobial susceptibilities are typically not known during this period. We refer to these first three days as the empiric period.

Participating hospitals are randomized to:

## • Arm 1 – Routine Care

## • Arm 2 – Real-Time Risk Estimation Smart Prompt

Precision medicine smart prompt using a computerized physician order entry (CPOE) alert that gives a patient-specific risk estimate of antibiotic resistant infection and recommends standard-spectrum antibiotics in patients admitted for UTI who are found to have low risk (<10%) for recovery of a drug resistant pathogen.

# **Trial Outcomes**

Trial outcomes evaluating intervention effectiveness are found in Table 1 below and trial safety outcomes are found in Table 2 below.

Outcome	Metric	
Primary Trial Outcome		
Extended-Spectrum Days Of Antibacterial Therapy (ES-DOT) per Empiric Day	The summed number of different extended-spectrum antibacterials received each empiric day, measured repeatedly over the first three days of an admission and divided by the number of empiric days of the admission. An empiric day is a day within the first three days of an admission. 	
Secondary Trial Outcomes		
Vancomycin Days of Antibacterial	The summed number of days of Vancomycin received each empiric	
Therapy per Empiric Day	day per at-risk-day (first 3 days of admission) 	
Antipseudomonal Antibiotic Days Of Therapy (ES-DOT) per Empiric Day	The summed number of different antipseudomonal antibacterials received each empiric day, measured repeatedly over the first three days of an admission and divided by the number of empiric days of the admission. An empiric day is a day within the first three days of an admission. 	

## Table 1: Primary and Secondary INSPIRE-ASP UTI Trial Outcomes

E.g., if a patient is admitted for 2 days, ES-DOT will be calculated for 2 days and divided by 2 empiric days; conversely if a patient is admitted for 4 days, only the first 3 days will be evaluated.

Does not include aminoglycosides or fluoroquinolones.

Safety outcomes planned for the primary manuscript are shown in Table 2. Safety outcomes will be analyzed separately from the main effectiveness outcomes of the trial (see Primary Statistical Analysis section below).

Table 2: Other Pre-Sp	ecified Outcomes – Safet	y Trial Outcomes
-----------------------	--------------------------	------------------

Safety Trial Outcomes (other pre-specified outcomes)		
Antibacterial Escalations [Safety	Days from start of standard-spectrum antibacterial until switch to extended-	
Outcome]	spectrum antibacterial during hospital stay	
ICU Transfers [Safety Outcome]	Days from start of hospitalization until ICU transfer within hospital stay	
Length-of-stay [Safety Outcome]	Days from hospital admission to discharge	

